4.3.2.4 Medically-Attended Adverse Events (MAAEs)

MAAE information will be collected throughout the study. MAAEs that occur from D0 to the D30 (+ 14 days) visit will be recorded as unsolicited AEs on the diary card as part of all unsolicited AEs collected for this post-vaccination period. An MAAE that occurs within the study period but meets the definition of an SAE should be reported only on the SAE Reporting Form, and not on the MAAE page of the CRF.

The Investigator will assess the causal relationship between the MAAE and the investigational or study product as either “Not related” or “Related,” as described in [Section 4.3.2.7](#).

4.3.2.5 Serious Adverse Events

Information on SAEs will be collected and assessed throughout the trial, from inclusion until 6 months after vaccination.

Any SAE occurring at any time during the trial will be reported by the Investigator through the electronic data capture (EDC) system and according to the completion guidelines provided by the Sponsor. All information concerning the SAE is to be reported, either as part of the initial reporting or during follow-up reporting if relevant information became available later (eg, outcome, medical history, results of investigations, copy of hospitalization reports. The Investigator will assess the causal relationship between the SAE and the investigational product as either “Not related” or “Related”, as described in protocol.

See protocol for further details on SAE reporting.

4.3.2.6 Adverse Events of Special Interest

The following AEs will be captured as AESIs throughout the study:

- Generalized seizures (febrile and non-febrile)
- Kawasaki disease
- Guillain-Barré syndrome
- Idiopathic thrombocytopenic purpura

These events have been listed as AESIs on the basis of the feedback received from the European Union regulators for other studies (conducted in younger age groups). No safety concerns relating to these AESIs have been identified with the use of MenACYW conjugate vaccine in the completed clinical trials. Because of their medical importance and to ensure expedited communication to the Sponsor, these AESIs are to be considered and collected as SAEs and reported to the Sponsor according to the procedure described in protocol. Further instructions on the data collection for these events and the relevant definitions will be provided in the Operating Guidelines.

4.3.2.7 Assessment of Causality

The Investigator will assess the *causal relationship* between each unsolicited systemic AE and vaccination as either **not related** or **related**, based on the following definitions:

Not related – The AE is clearly / most probably caused by other etiologies such as an underlying condition, therapeutic intervention, or concomitant therapy; or the delay between vaccination and the onset of the AE is incompatible with a causal relationship; or the AE started before the first vaccination (screening phase, if applicable)

Related – There is a “reasonable possibility” that the AE was caused by the product administered, meaning that there is evidence or arguments to suggest a causal relationship

Note: By convention, all AEs reported at the injection site (whether solicited or unsolicited) and all solicited systemic AEs are considered to be related to the administered product and therefore are referred to as reactions and do not require the Investigator’s opinion on relatedness.

Adverse events likely to be related to the product, whether serious or not, that persist at the end of the study will be followed up by the Investigator until their complete disappearance or the stabilization of the subject’s condition. The Investigator will inform the Sponsor of the date of final disappearance of the event or the date of “chronicity” establishment.

4.4 Derived Endpoints: Calculation Methods

4.4.1 Immunogenicity

4.4.1.1 Computed Values for Analysis

To appropriately manage extreme values ($< \text{LLOQ}$ and $\geq \text{ULOQ}$) for analysis purposes, the following computational rule will be applied to the values provided in the clinical database for each BL drawn:

- If a value is $< \text{LLOQ}$, then use the computed value $\text{LLOQ}/2$
- If a value is between $\geq \text{LLOQ}$ and $< \text{ULOQ}$, then use the value
- If a value is $\geq \text{ULOQ}$, then use the computed value ULOQ

To appropriately manage replicate values for analysis purposes, the individual GM (geometric mean) of all values will be computed for each BL after managing extreme values as described as above.

4.4.1.2 Seroresponse

4.4.1.2.1 Seroresponse as Defined in MEQ00066

An hSBA vaccine seroresponse for serogroups A, C, W, and Y is defined as a post-vaccination titer $\geq 1:16$ for subjects with pre-vaccination titer $< 1:8$, or a post-vaccination titer ≥ 4 times the pre-vaccination titer for subjects with a pre-vaccination titer $\geq 1:8$.

An rSBA vaccine seroresponse is defined as a post-vaccination titer $\geq 1:32$ for subjects with pre-vaccination rSBA titer $< 1:8$, or a post-vaccination titer ≥ 4 times the pre-vaccination titer for subjects with pre-vaccination rSBA titer $\geq 1:8$.

4.4.1.2.2 Seroresponse as Defined in MET49

hSBA and rSBA vaccine seroresponse were defined in MET49 as presented in [Section 4.4.1.2.1](#).

4.4.1.2.3 Seroresponse as Defined in MET44

Both an hSBA and rSBA vaccine seroresponse for serogroups A, C, W, and Y were defined as a post-vaccination titer $\geq 1:8$ for subjects with pre-vaccination titer $< 1:8$, or a post-vaccination titer ≥ 4 times the pre-vaccination titer for subjects with a pre-vaccination titer $\geq 1:8$. These definitions were based on the latest regulatory recommendations at the time of MET44.

4.4.1.3 Seroprotection

4.4.1.3.1 Serogroups A, C, W and Y

hSBA vaccine seroprotection for serogroups A, C, W, and Y is defined as an hSBA titer $\geq 1:8$.

4.4.1.3.2 Tetanus

Tetanus seroprotective antibody level is defined as ≥ 0.1 IU/mL tetanus toxoid.

4.4.1.4 Fold-rise

The derived endpoint fold-rise is driven by both baseline and post-baseline computed values and will be computed using the FDA definition as follows. Generally, for extreme values, this algorithm minimizes the numerator and maximizes the denominator.

- If the baseline computed value is $<$ LLOQ and the post-baseline computed value is $<$ LLOQ then the fold-rise is 1
- If the baseline computed value is \geq LLOQ and the post-baseline computed value is \geq LLOQ then the fold-rise is post-baseline computed value / baseline computed value
- If the baseline computed value is \geq LLOQ and the post-baseline computed value is $<$ LLOQ then the fold-rise is (LLOQ/2)/baseline computed value
- If the baseline computed value is $<$ LLOQ and the post-baseline computed value is \geq LLOQ then the fold-rise is post-baseline computed value / LLOQ

If the computed value is \geq 4-fold rise, then the derived \geq 4-fold rise indicator will be "Yes" for that test, otherwise \geq 4-fold rise will be "No."

Note: If baseline or post-baseline is missing, then fold-rise is missing.

4.4.2 Safety

4.4.2.1 Solicited Reactions

A solicited reaction is an "expected" AR (sign or symptom) observed and reported under the conditions (nature and onset) prelisted in the protocol and CRB (e.g., injection site pain or headache occurring between Day 0 and Day 7 post-vaccination). By definition, solicited reactions are to be considered as being related to the product administered.

For injectable vaccines, solicited reactions can either be solicited injection site reactions or solicited systemic reactions.

4.4.2.1.1 Daily Intensity

All daily records for solicited reactions will be derived into daily intensity according to the following classification: None, Grade 1, Grade 2, Grade 3, or Missing.

For measurable injection site reactions (Erythema/Swelling):

Grade 1: ≥ 25 to ≤ 50 mm

Grade 2: ≥ 51 to ≤ 100 mm

Grade 3: > 100 mm

For measurable systemic reactions (Fever):

Grade 1: $\geq 38.0^{\circ}\text{C}$ to $\leq 38.4^{\circ}\text{C}$ **or** $\geq 100.4^{\circ}\text{F}$ to $\leq 101.1^{\circ}\text{F}$

Grade 2: $\geq 38.5^{\circ}\text{C}$ to $\leq 38.9^{\circ}\text{C}$ **or** $\geq 101.2^{\circ}\text{F}$ to $\leq 102.0^{\circ}\text{F}$

Grade 3: $\geq 39.0^{\circ}\text{C}$ **or** $\geq 102.1^{\circ}\text{F}$

For the derivation of daily intensity, the following sequential steps will be applied:

- 1) Solicited reactions (except fever/pyrexia) with an investigator presence recorded as "No" and with all daily records missing, then all daily intensities will be derived as None.
- 2) For a temperature value that is partially missing after decimal point, the data will be analyzed replacing "MD" (missing data) by zero. For example, a "39.MD" daily temperature will be considered as "39.0°C" at the time of analysis.
- 3) For non-measurable solicited reactions, the daily intensities will correspond to the daily records reported in the clinical database. For measurable solicited reactions, the daily measurements reported in the clinical database will be converted based upon the intensity scales defined in the protocol; this assumes that a reaction that is too large to measure (non measurable, "NM") is Grade 3. Note: The maximum intensity during the ongoing period is derived from the record of the maximum intensity/measurement after the end of the solicited period following the rule described above.

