4.4.2.1.3 Presence

Presence is derived from the maximum overall intensity on the period considered:

- None: No presence
- Grade 1, Grade 2, or Grade 3: Presence
- Missing: Missing presence

Subjects with at least one non-missing presence for a specific endpoint will be included in the analysis.

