4.4.2.1.7 Ongoing

Ongoing is derived from the last daily intensity of the solicited period computed as described in [Section 4.4.2.1.1](#) and the maximum intensity during the ongoing period. The Investigator's ongoing flag is not used because the measurement would determine the ongoing status of the reaction. Note: The intensity could be considered None (not a reaction) in the analysis despite being considered a reaction by the Investigator (e.g., fever $> 37.5^{\circ}\text{C}$ but $< 38^{\circ}\text{C}$). If the last daily intensity of the solicited period is at least Grade 1 and maximum intensity on the ongoing period is also at least Grade 1, then the reaction is considered ongoing.

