5.3 Handling of Missing Data and Outliers

5.3.1 Safety

No replacement will be done. In all subject listings, partial and missing data will be clearly indicated as missing.

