5.3.1.4 Intensity

For solicited reactions, missing intensities will be handled as described in [Section 4.4.2.1.1](#). For unsolicited non-serious AEs, missing intensities will remain missing and will not be imputed.

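### With all daily records missing, an investigator No is kept as a non-reactor but a Yes drops out, which lowers the reported rates of pain, headache, malaise and myalgia

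*SAP*

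**What the plan says.** Four places in the SAP together decide what happens to a solicited reaction with no daily record.

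- **Section 4.4.2.1.1, step 1.** The scope of the rule is given as "Solicited reactions (except fever/pyrexia) with an investigator presence recorded as" negative. Its condition on the diary data and its result are worded "and with all daily records missing, then all daily intensities will be derived as None". Fever is left out, and the answer Yes is not mentioned.
- **Section 4.4.2.1.1, step 3.** For non-measurable reactions, "the daily intensities will correspond to the daily records reported in the clinical database". Erythema, swelling and fever are graded from the daily measurements. Neither route yields a grade if nothing was recorded.
- **Section 4.4.2.1.3.** Presence follows the maximum intensity, with the line "Missing: Missing presence". The denominator rule is: "Subjects with at least one non-missing presence for a specific endpoint will be included in the analysis".
- **Sections 5.3.1 and 5.3.1.4.** The general safety rule is "No replacement will be done". On intensity, "For solicited reactions, missing intensities will be handled as described in" section 4.4.2.1.1, so nothing is added for Yes.

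Section 4.4.2.1.7 is also relevant: "The intensity could be considered None (not a reaction) in the analysis despite being considered a reaction by the Investigator". Its example is a temperature above 37.5°C but below 38°C.

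**The concern.** One information source, the investigator's presence answer, is accepted when it says there was no reaction and ignored when it says there was one. Among subjects with no daily record, known non-reactors stay in the table and reported reactors disappear from it.

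This differs from how the SAP treats similar gaps. Under section 4.4.2.2.1 an unsolicited AE counts as an event if it has a verbatim term and is not Grade 0, and under section 5.3.1.4 its missing intensity simply stays missing. An unsolicited headache of unknown grade is therefore counted, while a solicited headache answered Yes without a daily grade is not. Section 5.3.1.2 treats missing causality as related, and step 3 treats a reaction too large to measure as Grade 3; both resolve doubt conservatively. Step 1 is also itself a replacement, which fits poorly with the no-replacement statement in section 5.3.1.

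At stake are the solicited-reaction percentages and their 95% CIs for Groups 1 to 4, which section 5.1.3 lists among the safety results.

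**Working it through.** The SAP states no reaction rate and no expected number of subjects without daily records, so there is no figure to reproduce. The check covers the direction of the effect and its size under stated assumptions.

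**Following the rules for a subject with no daily records**

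| Investigator answer | Pain, headache, malaise, myalgia, erythema, swelling | Fever |
|---|---|---|
| No | None; non-reactor in the denominator | Missing; excluded |
| Yes | Missing; excluded | Missing; excluded |

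The asymmetry exists for six of the seven solicited reactions and not for fever.

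**Inputs**

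- N: subjects with daily records or an investigator answer for the reaction. The planned group sizes in section 5.5 are 180 (Groups 1 and 2) and 40 (Groups 3 and 4).
- a: reactors with daily records. Assumed: 72 of 180, or 16 of 40.
- y: subjects with Yes and no daily record. Not in the SAP, so varied.

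**Formulas**

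- Rate under the SAP: a/(N − y).
- Rate if a Yes counts as present: (a + y)/N.
- The first is smaller exactly when aN < (a + y)(N − y), that is, when y(N − a − y) > 0.

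So the SAP rate is strictly lower whenever there is at least one such Yes subject and at least one non-reactor. Enumerating all cases with N from 2 to 79 gives no exception.

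**Numbers**

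| N | a | y | SAP rate | Yes counted as present |
|---|---|---|---|---|
| 180 | 72 | 1 | 72/179 = 40.2% | 73/180 = 40.6% |
| 180 | 72 | 4 | 72/176 = 40.9% | 76/180 = 42.2% |
| 180 | 72 | 9 | 72/171 = 42.1% | 81/180 = 45.0% |
| 40 | 16 | 1 | 16/39 = 41.0% | 17/40 = 42.5% |
| 40 | 16 | 2 | 16/38 = 42.1% | 18/40 = 45.0% |

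At y = 0 the two rates are identical.

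**When a Yes is not always a Grade 1 reaction**

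For erythema and swelling the lowest grade starts at 25 mm, so a Yes may fall below it. If only a share q of the Yes subjects truly reached Grade 1, the correct rate is (a + qy)/N, and the SAP rate is too low only if q > a/(N − y). With a = 72, N = 180 and y = 4 the threshold is 72/176, about 41%. Below it, dropping these subjects makes the SAP rate too high. For pain, headache, malaise and myalgia no size threshold separates a reported reaction from Grade 1, so q = 1 is the natural value.

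**The case against.** **Blank records may be normal for a No.** Non-reactors may have no daily entries because there was nothing to grade. The fever exception fits this: section 4.3.2.3.2 asks for a temperature every day, so a blank temperature is truly missing. Section 4.3.2.3.1 uses similar form logic for immediate AEs, with details collected once presence is marked. The CRB is not shown, so this is plausible but not proven. It is a good reason to keep step 1 for No; it gives no reason to discard a Yes.

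It also rules out the mirror-image remedy of excluding No answers without records. Take an assumed 180 subjects with 18 measured reactors and 162 No answers, a share g of them blank. The true rate is 10%, but the remedy would report 18/(18 + 162(1 − g)): 11.0% at g = 10% and 18.2% at g = 50%.

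**A reader might infer that every solicited rate can only be biased downward.** The documents do not support that. Fever is outside step 1, and for erythema and swelling a Yes may be below threshold, as section 4.4.2.1.7 illustrates for fever.

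**A reader might also size the bias by assuming that one share m of subjects lacks records, whatever their answer.** The reported rate would then be p(1 − m)/(1 − mp), for example 38.8% for a true p = 40% at m = 5%. Nothing in the SAP supports equal missingness for Yes and No. Yes with no record at all may be a separate and rare gap, and y has to be counted directly.

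**Materiality.** The analyses are descriptive. At a rate of 40% the 95% CI half-width is roughly 1.96 × √(0.4 × 0.6/N): about 7 points at N = 180 and 15 at N = 40, larger than the shifts above. Missing data are marked in listings, and a data review precedes lock (section 5.6). This limits the weight of the point. It does not remove a one-directional rule, whose effect a confidence interval does not reflect.

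**Conclusion.** The point holds for pain, headache, malaise and myalgia. As written, the rules retain a No and lose a Yes when all daily records are missing, and the reported percentage is too low whenever such Yes subjects exist. This rests on two things: that the Yes is a true reaction, and that a Yes without records ends as Missing. The SAP does not spell out the second, but it is the only reading that step 3 and section 4.4.2.1.3 support.

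In the assumed examples the shortfall is 0.3 to 2.9 points for N = 180 (y from 1 to 9) and 1.5 to 2.9 points for N = 40 (y of 1 or 2). It is zero if y = 0, and the SAP gives no basis for predicting y. Fever is not affected, and for erythema and swelling the direction is open. The immunogenicity hypotheses are untouched. The rule is worth correcting because it is one-sided and cheap to repair, not because a large bias has been shown.

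**What to change.** Keep step 1 for No. In sections 4.4.2.1.1 and 4.4.2.1.3:

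1. For pain, headache, malaise and myalgia, add a step: an investigator Yes with all daily records missing counts as present, with intensity Missing, and enters numerator and denominator.
2. For erythema and swelling, show the rate twice, with such Yes subjects counted as present and as not present.
3. For each reaction and group, report the number of subjects with Yes and no daily record.
4. In section 5.3.1, name steps 1 and 2 of section 4.4.2.1.1 and the new step as exceptions to the no-replacement statement.

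The cost is a few sentences, a small programming change, a Missing row in the intensity tables and a second line for two reactions. Where affected subjects exist, the reported rates for the four subjective reactions will be slightly less favourable.

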4.4.2.1.2 Maximum Overall Intensity

Maximum overall intensity is derived from the daily intensities computed as described in [Section 4.4.2.1.1](#) and is calculated as the maximum of the daily intensities over the period considered.

4.4.2.1.3 Presence

Presence is derived from the maximum overall intensity on the period considered:

- None: No presence
- Grade 1, Grade 2, or Grade 3: Presence
- Missing: Missing presence

Subjects with at least one non-missing presence for a specific endpoint will be included in the analysis.

4.4.2.1.4 Time of Onset

Time of onset is derived from the daily intensities computed as described in [Section 4.4.2.1.1](#). It corresponds to the first day with intensity of Grade 1, Grade 2, or Grade 3.

Note: If a reaction is not continuous (i.e., reaction occurs over two separate periods of time intervened by at least one daily intensity Missing or None) then the time of onset is the first day of the first occurrence.

Categories for time to onset are as follows

- D0-D3

- D4-D7

4.4.2.1.5 Number of Days of Occurrence

Number of days of occurrence over the period considered is derived from the daily intensities computed as described [Section 4.4.2.1.1](#). It corresponds to the number of days with daily intensities of Grade 1, Grade 2, or Grade 3. Number of days of occurrence during the solicited period with a specified intensity may also be derived.

Categories for number of days of occurrence during the solicited period are as follows

- 1-3 days
- 4-7 days
- 8 days

4.4.2.1.6 Overall Number of Days of Occurrence

If a reaction is ongoing at the end of the solicited period, then the overall number of days of occurrence is derived from the daily intensities and the stop date of the reaction after the end of the solicited period. The overall number of days of occurrence is:

- (stop date – last vaccination date) + (number of days of occurrence within the solicited period) – length of the solicited period + 1

If the stop date is missing or incomplete (contains missing data [MD]), the overall number of days of occurrence will be considered as Missing.

Categories for overall number of days of occurrence are as follows

- 1-3 days
- 4-7 days
- ≥ 8 days
- Missing

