4.3.2.3.2 Reactogenicity (Solicited Reactions from Day 0 to Day 7 after Vaccination)

After vaccination, subjects in Groups 1 to 4 will be provided with a diary card, a digital thermometer, and a flexible ruler, and will be instructed how to use them. The following items will be recorded by the subjects in the diary card on the day of vaccination and for the next 7 days (i.e., Day 0 through Day 7) until resolution:

- Daily temperature, with the route by which it was taken
- Daily measurement or intensity grade of all other solicited injection site and systemic reactions
- Action taken for each event (e.g., medication)

The action(s) taken by the subject to treat and/or manage any **solicited reactions** will be classified in the CRB using the following list (all applicable items should be checked):

- None
- Medication
- Health care provider contact
- Hospitalized

Subjects will be contacted by telephone 8 days after vaccination to remind them to record all safety information in the diary card.

If the timing of the telephone call should fall on a weekend or a holiday, the call should be made on the next business day. If contact is not made on the designated day, study staff will continue calling until contact is made. Every telephone attempt and its outcome will be documented in the source document.

[Table 4.1](#) and [Table 4.2](#) present, respectively, the injection site reactions and systemic reactions that are prelisted in the diary cards and CRB, together with the intensity scales.

Table 4.1: Solicited Injection Site Reactions: Terminology, Definitions, and Intensity Scales

CRB term (MedDRA lowest level term [LLT])	Injection site pain	Injection site erythema	Injection site swelling
Diary card term	Pain	Redness	Swelling
Definition	Pain either present spontaneously or when the injection site is touched or injected limb is mobilized	Presence of a redness including the approximate point of needle entry	Swelling at or near the injection site Swelling or edema is caused by a fluid infiltration in tissue or cavity and, depending on the space available for the fluid to disperse, swelling may be either soft (typically) or firm (less typical) to touch and thus can be best described by looking at the size of the swelling

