4.3.2.3.3 Unsolicited Adverse Events

In addition to recording solicited reactions, subjects will be instructed to record any other medical events that may occur during the 30-day period after vaccination. Space will be provided in the diary card for this purpose.

Information on SAEs will be collected and assessed throughout the study, from inclusion until 30 days after vaccination. Any SAE occurring at any time during the study will be reported by the Investigator in the CRB according to the completion instructions provided by the Sponsor; this includes checking the “Serious” box on the AE CRF and completing the appropriate Safety Complementary Information CRFs. All information concerning the SAE is to be reported either as part of the initial reporting or during follow-up reporting if relevant information became available later (e.g., outcome, medical history, results of investigations, copy of hospitalization reports).

For each unsolicited AE (whether serious or non-serious), the following information is to be recorded:

- Start and stop dates^a
- Intensity of the event:

For measurable unsolicited AEs that are part of the list of solicited reactions, the size of the AE as well as the temperature for fever will be collected and analyzed based on the corresponding scale used for solicited reactions (see [Table 4.1](#) and [Table 4.2](#)).

All other unsolicited AEs will be classified according to the following intensity scale:

- Grade 1: A type of AE that is usually transient and may require only minimal treatment or therapeutic intervention. The event does not generally interfere with usual activities of daily living.
- Grade 2: A type of AE that is usually alleviated with additional therapeutic intervention. The event interferes with usual activities of daily living, causing discomfort but poses no significant or permanent risk of harm to the research participant.

^a The stop date of all related AEs will be actively solicited. For other events, the investigator will provide the stop date when it becomes available. AEs for which no stop date was obtained during the course of the study will be considered as ongoing at the end of the study.

- Grade 3: A type of AE that interrupts usual activities of daily living, or significantly affects clinical status, or may require intensive therapeutic intervention.

- Whether the AE was related to the investigational product (for unsolicited systemic AEs)

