4.4.2.2.4 Time of Onset

Time of onset is derived from the start date of the unsolicited non-serious AE provided in the clinical database and the date of last vaccination:

- start date of the unsolicited non-serious AE – date of previous vaccination

The time of onset should be considered as missing only if one or both of the dates are missing or partially missing.

Unsolicited non-serious AEs will be analyzed “Within 30 days,” which corresponds to AEs with a time of onset between D0 and D30 days after vaccination or missing. An AE with missing time of onset will be considered to have occurred just after the vaccination indicated by the visit number, so will be included in these tables.

Note: Unsolicited non-serious AE that occurred before vaccination (negative time of onset) or with a time of onset beyond 30 days, will not be included in analysis; but will be listed separately.

Time of onset will be displayed as follows:

- D0-D3
- D4-D7
- D8-D14
- \geq D15
- Missing

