4.4.2.2.5 Duration

Duration is derived from the start and stop dates of the unsolicited non-serious AE provided in the clinical database:

- stop date of unsolicited non-serious AE - start date of unsolicited non-serious AE + 1.

The duration should be considered as missing only if the start and / or stop date of the unsolicited non-serious AE is missing or partially missing.

Duration will be displayed by period as following:

- 1-3 days
- 4-7 days
- 8-14 days
- \geq 15 days
- Missing

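### The duration rules put every event without a complete stop date in Missing, even where recorded data already establish the longest duration category

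*SAP*

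**What the plan says.** Section 4.4.2.1.6 derives the overall number of days for a solicited reaction that is ongoing when the solicited period ends. Its display categories are 1-3, 4-7, ≥ 8 days and Missing. On stop dates it says: "If the stop date is missing or incomplete (contains missing data [MD]), the overall number of days of occurrence will be considered as Missing".

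Section 4.4.2.2.5 defines the duration of an unsolicited non-serious event as "stop date of unsolicited non-serious AE - start date of unsolicited non-serious AE + 1". Its categories are 1-3, 4-7, 8-14, ≥ 15 days and Missing. It says: "The duration should be considered as missing only if the start and / or stop date of the unsolicited non-serious AE is missing", and it treats partial dates the same way. Sections 4.4.2.3.3 (SAEs) and 4.4.2.4.3 (MAAEs) reuse this method.

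Section 5.3.1.5 says that stop dates are not imputed. Footnote a of section 4.3.2.3.3, in the text on unsolicited events, gives an absent stop date a meaning: "AEs for which no stop date was obtained during the course of the study will be considered as ongoing at the end of the study". Neither duration display has a category for events that are still ongoing.

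**The concern.** A stop date can be absent for two different reasons: the event had not resolved, or it resolved and the date was not captured or is incomplete. Under the plan both go into one cell. In the first case the duration is not unknown in the ordinary sense. It has a minimum, and that minimum can already lie in the longest category.

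The absence is then partly caused by the outcome, because an event that does not resolve produces no stop date. Section 4.3.2.2 names the number of days of occurrence (solicited reactions) and the duration (unsolicited events and SAEs) among the safety endpoints, and Table 5.2 tabulates duration. A reader who looks there for persistent reactions after revaccination would see too few in the longest category and could not tell from that table how many of the Missing events were unresolved.

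**Working it through.** The SAP states no figure to reproduce here, so the check applies its own formulas. The last day on which the event is recorded as present stands in for the stop date, which gives a lower bound on the duration.

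**Inputs**
- Solicited period: D0 to D7, so its length is 8 days (sections 4.3.2.3.2 and 4.4.2.1.5).
- Solicited formula (4.4.2.1.6): (stop date − vaccination date) + k − 8 + 1, where k is the "number of days of occurrence within the solicited period".
- Ongoing reaction (4.4.2.1.7): at least Grade 1 on D7 and at least Grade 1 in the period after it. Hence k is at least 1, and the reaction reaches at least D8.
- Unsolicited formula (4.4.2.2.5): stop day − onset day + 1.
- Onset window for unsolicited events (4.4.2.2.4): "AEs with a time of onset between D0 and D30 days after vaccination or missing".
- Last visit: D30 to D44 after vaccination (Tables 3.2 to 3.4).

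**Formula check.** A continuous reaction from D0 to day d, with d after D7, gives d + 8 − 8 + 1 = d + 1 days, as it should.

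**Solicited reactions, lower bound = e + k − 8 + 1, with e the last day recorded as ongoing**

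| Last day recorded as ongoing | k = 1 | k = 8 | ≥ 8 days certain? |
|---|---|---|---|
| D8 | 2 | 9 | only for k of 7 or 8 |
| D10 | 4 | 11 | only for k of 5 or more |
| D14 | 8 | 15 | yes, for every k |
| D30 | 24 | 31 | yes |
| D44 | 38 | 45 | yes |

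The first row needs no visit date. With k = 7 and presence on D8, the bound is 8 + 7 − 8 + 1 = 8. So any reaction with 7 or 8 reaction days that meets the section 4.4.2.1.7 definition of ongoing is already in ≥ 8 days.

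For k = 8 the plan's own tables diverge. Section 4.4.2.1.5 puts the subject in the 8 days category for the solicited period. Section 4.4.2.1.6 puts the same reaction in Missing if there is no complete stop date.

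**Unsolicited events, lower bound = e − s + 1, with s the onset day.** This is at least 15 exactly when s is at most e − 14.

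| Last visit, event recorded as ongoing | Onset days for which ≥ 15 days is certain |
|---|---|
| D30 | D0–D16 (17 of 31 onset days) |
| D37 | D0–D23 (24 of 31) |
| D44 | D0–D30 (all 31) |

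At a D30 visit the bound is 8 to 14 days for onset D17–D23, 4 to 7 days for D24–D27, and 1 to 3 days for D28–D30.

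**Direction.** Let a events have a known longest duration, b a known shorter duration, m a longest duration that is certain but coded Missing, and u an unknown duration. If Missing is in the denominator, the plan reports a/(a + b + m + u) where (a + m)/(a + b + m + u) is certain. If Missing is left out, it reports a/(a + b) where (a + m)/(a + b + m) could be reported. Whenever m and b are above zero, the plan's figure is lower in both cases.

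**The case against.** The strongest defence has four parts.

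- **The rule is explicit and consistent.** Section 5.3.1.5 imputes no stop dates, and Missing assigns no wrong duration. This stands as a description, but it does not answer the point: assigning a category from an established lower bound imputes no date.
- **Few events may be affected.** Footnote a also says that stop dates of related events will be actively sought. All solicited reactions count as related, and section 4.3.2.7 has related events that persist at study end followed until they disappear or stabilise. This stands and reduces the number affected. It does not remove the problem: unrelated events are not actively pursued, and follow-up may end with a date of chronicity, for which no duration rule is given.
- **Other outputs carry part of the information.** Section 4.4.2.1.7 derives an ongoing variable for solicited reactions, section 4.4.2.1.5 covers D0–D7 without a stop date, and Table 5.2 lists outcome for SAEs and MAAEs. This stands. Among the outputs listed, non-serious unsolicited events in general have no such indicator.
- **An absent stop date does not show that an event was unresolved.** Footnote a is a convention and sits in the text on unsolicited events. It also covers events that ended without the date being captured. This stands and limits the remedy: the bound must rest on a record that the event was present.

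A reader might infer that the dates place every event without a stop date in the longest category. They do not: late-onset unsolicited events and subjects who leave early are counterexamples. A reader might also infer that the tables drop exactly the events that did not resolve. They do not: those events stay in the counts under Missing, beside resolved events with partial dates and unsolicited events with missing start dates. Nor do footnote a and the duration rules contradict each other outright, since an event can be ongoing and have an unknown exact duration.

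**Conclusion.** The point holds in a limited form. Sections 4.4.2.1.6 and 4.4.2.2.5 pool unresolved events with events of unknown date, even when the longest category is already established. That is so in three situations:

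- a solicited reaction with at least 7 reaction days in D0–D7 that continues past D7;
- a solicited reaction recorded as ongoing at D14 or later;
- an unsolicited event recorded as ongoing at least 14 days after onset.

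The result is a downward bias in the ≥ 8 days and ≥ 15 days categories. Its size is unknown, because the SAP gives no count of such events. The conclusion assumes that presence or ongoing status on the relevant day is actually recorded. It concerns descriptive safety tables only and leaves the primary and secondary hypothesis tests untouched. It is worth correcting because the direction is predictable and duration is a named endpoint.

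**What to change.** In sections 4.4.2.1.6 and 4.4.2.2.5 (and so for SAEs and MAAEs), add a rule for events with no stop date:

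1. Compute a lower bound on duration from the last date on which the event is recorded as present or ongoing (daily records, the ongoing-period record, or the last visit). Do not infer it from the absence of a stop date alone.
2. Assign ≥ 8 days (solicited) or ≥ 15 days (unsolicited, SAE, MAAE) when the bound reaches that category.
3. Show other events recorded as unresolved in a new category, Ongoing at last contact.
4. Keep Missing for unknown or partial dates.

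The text should name the data source for ongoing status, because section 4.4.2.1.7 sets the investigator's ongoing flag aside and its own variable carries no visit date. Section 5.3.1.5 can stay as it is. The cost is a few lines of SAP text and one extra derivation, and the longest-duration percentages become slightly less favourable.
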